#### 9.3 Adverse Events

In a 7 week, randomized, placebo controlled trial comparing JNJ-18038683 with placebo and escitalopram (an active comparator), a total of 6 serious adverse events were reported during the study (placebo group: spontaneous abortion and suicidal ideation; escitalopram group: spontaneous abortion, suicidal ideation, suicide attempt, and chest discomfort). A total of 10 individuals (3 in the placebo group, 4 in the JNJ-18038683 group, and 3 in the escitalopram group) were withdrawn from the study prematurely due to adverse events. The 4 events leading to drop out of individuals on JNJ-18038683 were one instance each of the following: bundle branch block, panic attack, upper respiratory infection, and insomnia.

Only 3 individuals receiving the 20-mg dose of JNJ 18038683 required dose reductions at any point during the study.

Adverse events that were reported in more than 5% of individuals in any treatment group included headache, nausea, nasopharyngitis, insomnia, somnolence, dyspepsia, dizziness, dry mouth, constipation, diarrhea, vomiting, back pain, upper respiratory tract infection, palpitations, and fatigue. The treatment-emergent adverse events that were reported more frequently in the JNJ 18038683 group compared with the placebo or escitalopram groups included dyspepsia, constipation, upper respiratory tract infection, and palpitations.

#### 9.3.1 Contraindications:

None known

#### 9.3.2 Special Warnings and Precautions for Use

JNJ-18038683 is an investigational drug, with safety data available from nonclinical animal studies, as well as single and multiple dose clinical studies in healthy volunteers.

All individuals should be closely monitored by means of adverse events, vital signs, ECGs, and clinical laboratory safety tests of blood and urine.

The liver, lung, prostate, mammary gland, hematologic system, and thymus in rats (mainly at high dose), and the hematologic system and spleen in dogs, were identified as potential target organs for JNJ-18038683 in repeat-dose oral toxicity studies (see Other Effects in Investigator Brochure). Female animals appeared to be more susceptible than males.

Thus far in clinical trials, there have been no laboratory abnormalities of concern, but the following safety tests should be monitored:

- Hematologic parameters: red blood cell (RBC), hemoglobin, hematocrit, unconjugated bilirubin, reticulocyte, and platelet counts;
- Liver function: aspartate transaminase (AST), alanine transaminase (ALT), gamma glutamyltransferase (GGT), prothrombin time, total bilirubin, lactic dehydrogenase, serum albumin, and protein.

#### 9.3.3 Interaction with other medications

After single and multiple doses of JNJ-18038683, limited or no inhibition of CYP3A4 and CYP2C9 activity may be expected, while moderate inhibition of CYP2C19 activity, and strong inhibition of CYP2D6 activity may be likely. JNJ-18038683 increased the rate of T4 glucuronidation. There was no induction of CYPs 1A2, 3A4, 2C9, and 2C19 by JNJ-18038683.

#### 9.3.4 Adverse Event Monitoring

Adverse event data collection and reporting, which are required as part of every clinical trial, are done to ensure the safety of individuals enrolled in the studies as

well as those who will enroll in future studies using similar agents. Adverse events are reported in a routine manner at scheduled times during a trial. Additionally, certain adverse events must be reported in an expedited manner to allow for optimal monitoring of patient safety and care.

All individuals experiencing an adverse event, regardless of its relationship to study drug, will be monitored until:

- the adverse event resolves or the symptoms or signs that constitute the adverse event return to baseline;
- any abnormal laboratory values have returned to baseline;
- there is a satisfactory explanation other than the study drug for the changes observed; or
- death.

#### 9.3.5 Definitions

#### 9.3.5.1 Definition of Adverse Event

An adverse event (AE) is any untoward medical occurrence in a patient receiving study treatment and which does not necessarily have a causal relationship with this treatment. An AE can therefore be any unfavorable and unintended sign (including an abnormal laboratory finding), symptom, or disease temporally associated with the use of an experimental intervention, whether or not related to the intervention.

#### 9.3.5.2 Severity of Adverse Events

The severity of an AE is graded as follows:

Mild (grade 1): the event causes discomfort without disruption of normal daily activities.

Moderate (grade 2): the event causes discomfort that affects normal daily activities.

Severe (grade 3): the event makes the patient unable to perform normal daily activities or significantly affects his/her clinical status.

Life-threatening (grade 4): the patient was at risk of death at the time of the event.

Fatal (grade 5): the event caused death.

#### 9.3.5.3 Serious Adverse Events

A "serious" adverse event is defined in regulatory terminology as any untoward medical occurrence that:

#### Results in death.

 If death results from (progression of) the disease, the disease should be reported as event (SAE) itself.

#### Is life-threatening.

- (the patient was at risk of death at the time of the event; it does not refer to an event that hypothetically might have caused death if it were more severe).
- Requires in-patient hospitalization or prolongation of existing hospitalization for ≥ 24 hours.
- Results in persistent or significant disability or incapacity.
- Is a congenital anomaly/birth defect
- Is an important medical event

Any event that does not meet the above criteria, but that in the judgment of the investigator jeopardizes the patient, may be considered for reporting as a serious adverse event. The event may require medical or surgical intervention to prevent one of the outcomes listed in the definition of "Serious Adverse Event".

For example: allergic bronchospasm requiring intensive treatment in an emergency room or at home; convulsions that may not result in hospitalization; development of drug abuse or drug dependency.

# 9.3.6 Steps to Determine If an Adverse Event Requires Expedited Reporting

Step 1: Identify the type of adverse event

Step 2: Grade the adverse event

Step 3: Determine whether the adverse event is related to the protocol therapy Attribution categories are as follows:

- Definite The AE is clearly related to the study treatment.
- Probable The AE is likely related to the study treatment.
- Possible The AE may be related to the study treatment.
- Unrelated The AE is clearly NOT related to the study treatment.

Note: This includes all events that occur within 30 days of the last dose of protocol treatment. Any event that occurs more than 30 days after the last dose of treatment and is attributed (possibly, probably, or definitely) to the agent(s) must also be reported accordingly.

Step 4: Determine the prior experience of the adverse event.

Expected events are those that have been previously identified as resulting from administration of the agent. An adverse event is considered unexpected, for expedited reporting purposes only, when either the type of event or the severity of the event is not listed in:

- the current known adverse events listed in the Agent Information Section of this protocol;
- the GRAS dossier for the supplement;

### 9.3.7 Reporting Requirements for Adverse Events

#### **Expedited Reporting**

- The Principal Investigator must be notified within 24 hours of learning of any serious adverse events, regardless of attribution, occurring during the study or within 30 days of the last administration of the study drug.
- The investigator or site personnel will inform Janssen within 24 hours of notification of any serious adverse event by phone or fax, with follow-up with a written narrative of the event within 48 hours.
- The Northwestern University Institutional Review Board must be notified within 10 business days of "any unanticipated problems involving risk to individuals or others"

The following events meet the definition of Unanticipated Problem Reporting (UPR):

- 1. Any serious event (injuries, side effects, deaths or other problems), which in the opinion of the Principal Investigator was unanticipated, involved risk to individuals or others, and was possibly related to the research procedures.
- 2. Any serious accidental or unintentional change to the IRB-approved protocol that alters the level of risk.
- 3. Any deviation from the protocol taken without prior IRB review to eliminate apparent immediate hazard to a research subject.
- 4. Any new information (e.g., publication, safety monitoring report, updated sponsor safety report), interim result or other finding that indicates an unexpected change to the risk/benefit ratio for the research.
- 5. Any breach in confidentiality that may involve risk to the subject or others.
- 6. Any complaint of a subject that indicates an unanticipated risk or that cannot be resolved by the Principal Investigator.
- The FDA will be notified within 7 business days of any unexpected fatal or life-threatening adverse event with possible relationship to study drug, and 15 business days of any event that is considered: 1) serious, 2) unexpected, and 3) at least possibly related to study participation.

#### **Routine Reporting**

• All other adverse events- such as those that are expected, or are unlikely or definitely not related to the study participation- are to be reported annually to the Northwestern IRB as part of regular data submission.

#### 9.3.8 Unblinding Procedures

The blind should not be broken unless subject has completed all study procedures and the data has been locked. Emergency unblinding is expected to be infrequent.

Emergency unblinding should occur only if the principal investigator (or other treating physician) considers breaking the blind medically relevant. All individuals who have the blind broken will be discontinued from the study. Documentation of the reasons for unblinding, including date and time will be recorded in the source documents and the electronic case report form (eCRF).

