Individuals will be asked to return to the clinic at study weeks 1, 2, 4, and 6 after baseline to monitor for side effects and compliance. At the Week 4 visit, efficacy assessments will be completed (MADRS, YMRS and CGI-BP). Between clinic visits, research staff will complete phone calls with individuals at study Weeks 3, 5, and 7. Individuals will return for a final study visit 8 weeks after initiation of the randomized study medication. A Safety Follow-up phone call will take place 4 weeks after the final visit and safety assessments will be completed (C-SSRS, Adverse Events, Concomitant Medications). The assessments completed at baseline will be repeated at this Week 8 visit (See Appendix 1 – Schedule of Assessments). Reasons for early termination will be recorded. Every effort will be made to obtain appropriate rating scale data at the final visit of early terminators.

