#### 9.4.8 Physical Examination

The physical exams must be performed by the PI or designee (or a licensed medical practitioner such as a physician's assistant or nurse practitioner) listed on the site delegation of authority log.

A complete physical examination includes the following assessments: general appearance, head, eyes, ears/nose/throat, neck, lymph nodes, skin, lungs, heart, abdomen, musculoskeletal, and neurologic evaluations. If the subject is discontinued for any reason during the treatment phase, every attempt should be made to perform a final physical examination.

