#### 13.0 Withdrawal of Individuals\*

Individuals can be taken off the study treatment and/or study at any time at their own request, or they may be withdrawn at the discretion of the investigator for safety, behavioral or administrative reasons. The reason(s) for discontinuation will be documented and may include:

- Individual voluntarily withdraws from treatment (follow-up permitted);
- Individual withdraws consent (termination of treatment and follow-up);
- Individual is unable to comply with protocol requirements;
- Individual experiences toxicity that makes continuation in the protocol unsafe:
- Physician judges continuation on the study would not be in the patient's best interest;
- Individual becomes pregnant (pregnancy to be reported along same timelines as a serious adverse event).

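### Breaking the blind ends study participation, with no provision to collect the Day 56 primary assessment or make the Day 84 safety call

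*Protocol*

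**What the plan says.** Protocol 9.3.8 sets the trigger: "Emergency unblinding should occur only if the principal investigator (or other treating physician) considers breaking the blind medically relevant". It adds that "Emergency unblinding is expected to be infrequent" and gives the consequence: "All individuals who have the blind broken will be discontinued from the study". It contains no clause on later assessments.

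Protocol 13.0 treats leaving treatment and leaving the study as different things. One listed reason is "Individual voluntarily withdraws from treatment (follow-up permitted"; withdrawal of consent, which ends both treatment and follow-up, is a separate item. Unblinding is not on the list.

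On data from patients who leave early, protocol 9.0 says: "Every effort will be made to obtain appropriate rating scale data at the final visit of early terminators". Protocol 9.4.8 says: "If the subject is discontinued for any reason during the treatment phase, every attempt should be made to perform a final physical examination".

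On adverse events, protocol 9.3.4 opens its follow-up rule with "All individuals experiencing an adverse event, regardless of its relationship to study drug, will be monitored until" and lists resolution, return to baseline, another explanation, or death. Protocol 9.3.6 adds: "This includes all events that occur within 30 days of the last dose of protocol treatment". Protocol 9.4.11, however, ends adverse-event recording when the subject has discontinued or completed the study.

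The SAP makes the 8-week evaluation the primary outcome, tabulates dropouts with reasons, and fills missing evaluations by carrying the last value forward. Protocol 11.1 names MMRM instead. The SAP does not mention unblinded patients.

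**The concern.** A patient whose code is broken has not withdrawn anything. A physician has judged that knowing the allocation matters for care. Ending that patient's participation gives up the scheduled primary assessment for a reason that arises from a clinical event and may be related to treatment. This is missingness that neither a carried-forward value nor a model assuming data missing at random handles well.

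The design offers little to fall back on. There is one planned post-baseline cognitive assessment, so an early exit leaves no scheduled intermediate value. The Day 84 call, which covers C-SSRS, adverse events and concomitant medication, is not stated to apply to these patients. Sites would also have to choose between sections that disagree on how long adverse events are recorded.

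**Working it through.** **1. The plan's own figure.** Inputs from protocol 11.1: difference 5 points, SD 9.4, correlation 0.5, compound symmetry, 2 time points, alpha 0.05, power 80%.

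- SD of the time-averaged value: 9.4 × √((1 + 0.5)/2) = 8.141.
- One-sided: 33 per group, power 0.8024. The protocol prints 33 and 0.80235.
- Two-sided: 42 per group, power 0.8036. The protocol gives 42.

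Both sample sizes reproduce. The planned enrolment is 30 per arm (protocol 22.0), and that is the base used below.

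**2. Cognitive values available after an early exit.** Protocol 9.4.2, Appendix 1 and SAP Table 2 place the battery at baseline and Day 56. The table in protocol 7.0 also marks it at screening, which adds no post-baseline value. The only possible source is therefore the exit visit in protocol 9.0. That provision is best effort, refers to rating scale data without naming the cognitive battery, and yields a value at exit rather than at Day 56. Neither schedule of assessments has an early-termination column.

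**3. What the missing-data rules then do.**

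- *Last value carried forward (SAP):* with no exit battery, the last value is baseline, so change = 0. With an exit battery, that value can be carried instead.
- *MMRM (protocol 11.1):* there is no intermediate cognitive value to inform the estimate.

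**4. Size.** The documents give no unblinding rate, so assume k = 0 to 3 patients in the active arm without a Day 56 value.

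- Shift in the arm mean if each is scored 0 when the true change would have been 5: 5k/30.
- Power if the values are simply absent: standard error = 8.141 × √(1/(30 − k) + 1/30).

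| k | Share of arm | Shift in mean (points) | Share of 5-point effect | Power, one-sided | Power, two-sided |
|---|---|---|---|---|---|
| 0 | 0% | 0 | 0% | 76.9% | 66.2% |
| 1 | 3.3% | 0.17 | 3.3% | 76.2% | 65.5% |
| 2 | 6.7% | 0.33 | 6.7% | 75.6% | 64.7% |
| 3 | 10% | 0.50 | 10% | 74.9% | 63.9% |

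Per patient the shift is 0.17/9.4 = 0.018 SD. In the placebo arm, where the plan assumes no improvement, scoring zero change shifts the mean by 0 on the plan's own assumption.

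**5. Safety provisions side by side.**

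| Section | After discontinuation |
|---|---|
| 9.3.4 | Monitoring continues to a stated end point |
| 9.3.6, 9.3.7 | Events to 30 days after last dose are covered |
| 9.4.8 | Final physical examination attempted |
| 9.4.11 | Recording ends at discontinuation, yet causally related events are followed until resolved or stable |
| 9.0 | Adverse events collected to the final safety follow-up; Day 84 call not expressly kept for unblinded patients |

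These cannot all be followed for a patient discontinued under 9.3.8.

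**The case against.** A reader might infer several stronger things that the documents do not support.

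- *Outcomes are lost in the patients with the most serious events.* The trigger is medical relevance as judged by a physician, not grade or seriousness, and the serious-event procedures never require unblinding. Loss of all outcomes is not established either, because unblinded patients are early terminators and protocol 9.0 seeks exit data from them.
- *Safety follow-up is cut.* Sections 9.3.4, 9.3.6, 9.3.7 and 9.4.8 all continue some form of it. The defect is contradiction, not absence.
- *These patients are all scored as unchanged.* That holds only if no exit battery is obtained and the carry-forward rule is applied. The SAP sentence follows the description of the mixed model, and it is unclear whether it also governs the primary ANCOVA. The rule affects every dropout, so it is not specific to unblinding.
- *The loss falls more on the active arm.* Nothing shows this. In the earlier trial described in protocol 9.3, adverse-event withdrawals were 3 on placebo, 4 on JNJ-18038683 and 3 on escitalopram, and none of the 6 serious events was in the JNJ-18038683 group. Arm sizes are not given.

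It can also be said that study exit after unblinding is compatible with Section 13.0, whose list of reasons is not exhaustive, and that ratings made after unblinding are open to bias.

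All of this narrows the point. It does not supply a provision for the Day 56 battery or the Day 84 call, and it leaves the adverse-event sections in conflict.

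**Conclusion.** The point holds in limited form. Section 9.3.8 is an explicit rule that ends study participation, and following it gives up the scheduled primary value for a clinically driven reason. The exit-data provision is only a partial safeguard.

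The size is small. The 0.17 points per active-arm patient is an upper-end illustration: it assumes no exit value, zero change imputed, and a full 5-point gain otherwise. A patient who stops drug early need not show that gain, so collecting the Day 56 value might recover less. Even three such patients would cost about 2 percentage points of power. The reason to act is avoidable informative missingness and inconsistent site instructions, not power. This is a cheap improvement rather than a threat to the trial's conclusion.

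**What to change.** **Protocol.** Leave the treatment decision after unblinding as it stands. Reconcile 9.3.8 with 9.0, 9.3.4, 9.4.11 and 13.0 by stating that unblinded patients who have not withdrawn consent stay in outcome assessment through Day 56, including the cognitive battery, and in safety assessment through the Day 84 call. Make the end of adverse-event recording the same in every section.

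**SAP.** State that unblinded patients are analysed in their randomised arm, that any rating made after unblinding carries a flag, and that a sensitivity analysis excludes those ratings.

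**Cost.** About one sentence in each document, plus the visits of a few patients. The downside is a small number of ratings made with knowledge of treatment, which matters most for clinician-rated scales such as MADRS, CGI-BP and SLOF. A flag identifies those ratings but does not remove the bias, which is why the sensitivity analysis is needed.

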#### 9.4 Study Materials

#### 9.4.1 Structured Clinical Interview for DSM-IV (SCID)

The SCID-CT is a short semi-structured interview. With an administration time of approximately 15 minutes, it was designed to meet the need for a short but accurate structured psychiatric interview for multicenter clinical trials and epidemiology. The SCID-CT will be administered by raters at the study site. The SCID-CT must be administered by a site study staff member listed on the site delegation of authority log with at least 2 years of experience with the population under study. The results of this assessment will be used to confirm the diagnosis of bipolar disorder I or II and rule out any exclusionary diagnosis. The SCID will be administered at the screening visit.

#### 9.4.2 Cognition battery

The "Cleveland" cognition battery will be administered in this trial, which the PI has used over the past 30+ years as measures of the following cognitive domains: executive functioning, speed of processing, attention/vigilance, working memory, verbal learning, visual learning, reasoning and problem solving

This battery includes the following assessments:

- Wisconsin Card Sorting Test (WCST)
- Digit Symbol Task
- Rey Auditory Verbal Learning Test (Rey-AVLT)
- WISC-III Mazes
- Category Fluency Test
- Verbal Fluency

18

Brown-Peterson Consonant Trigram Memory Task

The cognition battery will be administered at baseline and end of study.

#### 9.4.3 Montgomery Asberg Depression Rating Scale (MADRS) [35] -

The MADRS will be utilized to assess a subject's level of depressive symptoms and must be administered using a structured interview guide. This scale consists of 10 items each with 7 defined grades of severity

#### 9.4.4 Young Mania Rating Scale (YMRS) [36]-

The YMRS consists of 11 items assessing the core symptoms of mania and is based on the subject's subjective report of his or her clinical condition. Additional information is based upon clinical observations made during the course of the clinical interview. Each item has 5 defined categories of severity with 4 items graded on a 0 to 8 scale (irritability, speech, content, and disruptive-aggressive behavior) and 7 items graded on a 0 to 4 scale.

#### 9.4.6 Clinical Global Impression Scale - Bipolar (CGI-BP) [37] -

The CGI-BP scale refers to the global impression of the subject with respect to bipolar disorder. The scale rates the subject's Severity of Illness (CGI-BP-Severity: mania, depression, and overall bipolar illness) and Change from Preceding Phase (CGI-BP Change from Preceding Phase: mania, depression, and overall bipolar illness) based on a 7-point scale. Severity of Illness (CGI-BP-Severity) will be rated at the baseline visit. The Change from Preceding Phase (CGI-BP Change from Preceding Phase) will be rated at the end of study visit (Week 9).

